**Clinical Study Protocol** 

#### HS-15-549

#### **Braeburn Pharmaceuticals**

CONFIDENTIAL

Study Period/Phase:	Screening	Treatment Phase													
Treatment:		GI	DDN						160	mg CAM20	38 q4w				FU
		SL	BPN		D	ose 1	]	Dose 2	]	Dose 3			Dose 4		
Day:	-21 to -1	D1- D6	D7	D8	D9	D15 D22 D29	D36	D38, D43, D50, D57	D64	D66, D71, D78, D85	D92	D93	D94, D95, D96, D97, D99, D102, D106, D113	D120/ EOT	D127
Concomitant Medications/Procedures	Х	Х	Х	X	Х	Х	Х	Х	Х	Х	Х	Х	Х	Х	Х
C-SSRS i	Х	Х	Х	X	Х		X		X		Х			Х	
Injection Site Examination j				X	Х	Х	X	Х	Х	X	Х	Х	Х	Х	
PK samples			X k	Xk		X k	Xl	xl	x l	Xl	X m	X m	X m	X m	
COWS n		X	Х	X		Х	X	X	Х	X	X		X	Х	
sows n		Х	Х	X		Х	Х	X	Х	X	X		Х	Х	
UDS and breath alcohol test	Х	Х	Х	X	Х	Х	Х	X	Х	X	Х	Х	X	Х	
NRS for Pain o	Х	Х	Х	X	Х	Х	X	X	X	X	Х	Х	X	Х	
SL BPN administration		Х	Х												
CAM2038 q4w SC injection p				X			X		Х		X				
Admission to CRU			Х								X				
Discharge from CRU				Xq								Х			
Outpatient visits		Х			Х	Х	X	X	Х	X			X	Х	
Telephone call															X
Transfer to previous BPN therapy														Х	

C-SSRS-Screening will be performed at Screening and then C-SSRS-since last visit will be performed at other subsequent visits.

J Injection site examinations will occur at each visit after CAM2038 q4w administration and once daily during inpatient stays.

k Pharmacokinetic samples will be collected at pre-dose (within 45 minutes), 10, 20, 30 and 40 minutes, and 1, 1.5, 2, 3, 4, 6, 10 and 24 hours after SL BPN dose 7, and pre-dose, 168 hrs (7 days), 336 hrs (14 days) and 504 hrs (21 days) after CAM2038 q4w dose 1. If a subject terminates early from the study, then a PK blood sample is to be drawn.

 Pharmacokinetic samples will be collected at pre-dose, one sample any time between 4 and 8 hrs post-dose, approximately 48 hrs, 168 hrs (7 days), 336 hrs (14 days) and 504 hrs (21 days) after CAM2038 q4w doses 2 and 3.

m Pharmacokinetic samples will be collected at pre-dose, 0.5, 1, 2, 4, 6, 10, 24, 48, 72, 96, 120, 168 (7 days), 240 (10 days), 336 (14 days), 504 (21 days) and 672 (28 days) hours after CAM2038 q4w dose 4.

n COWS and SOWS will be performed pre-dose on all dosing days and at each other visit.

 Average daily NRS pain score will be recorded using an electronic device each day.

p The 4 SC injections will be administered in the buttock, rotating between right and left buttock and injection site per Appendix 17.2.

q Subjects will be discharged at least 6 hours after CAM2038 q4w dose 1, once the ECG and other safety assessments are completed, and the Investigator deems it safe for the subject to leave the CRU.

BMI=body mass index; BPN=buprenorphine; COWS=Clinical Opioid Withdrawal Scale; CRU=clinical research unit; C-SSRS=Columbia-Suicide Severity Rating Scale; D=day; ECG=electrocardiogram; EOT=End of Treatment; NRS=numerical rating scale; PK=pharmacokinetic; SC=subcutaneous; SL=sublingual; SOWS=Subjective Opioid Withdrawal Scale; UDS=urine drug screen.

### **10.1 Demographics and Other Baseline Characteristics**

#### **10.1.1 Informed Consent**

The nature of the study and its risks and benefits will be explained to the subject by the Investigator or designated study personnel. The subject must voluntarily provide written informed consent on an ethics-approved ICF, prior to performing any study-related procedures. The subject's medical records must document that the consent process has been completed and that written informed consent has been obtained from the subject prior to the initiation of any study-specific procedures. Documentation that the subject was given adequate time to ask the Investigator (or designee) questions about their participation in the study and that a signed and dated copy of the ICF was provided to the subject should also be included in the medical records or clinical chart.

#### **10.1.2 Demographics**

The following demographics will be recorded: age (birthdate), sex, weight, height, body mass index (BMI), race, and ethnicity.

#### 10.1.3 Medical and Psychosocial History

The complete medical history will include histories of acute, chronic, or infectious disease; surgical or oncologic histories; and any reported conditions affecting major body systems in the past five years or deemed to be clinically significant in the opinion of the Investigator. All findings on medical history will be evaluated by the Investigator for clinical significance.

A complete psychosocial history will be obtained including education, employment status, marital/significant other status, residential status and legal status/arrest history.

#### **10.1.4 Medication History**

All medications (prescription and non-prescription or herbal medications/natural health products) taken by the subjects during the 30 days prior to Screening will be recorded in the source documentation as medication history. Substance Use and Treatment History (Section 10.1.5) will be collected separately and stored in the subject's file.

#### 10.1.5 Substance Use and Treatment History

DSM-V modules will be included to evaluate alcohol and substance use disorders.

A complete history of previous and current illicit drug use, substance abuse/dependence, and treatments for any substance use disorders (pharmacologic as well as non-pharmacologic) will be obtained using a timeline follow-back type of interview (Fals-Stewart et al., 2000).

### 10.2 Eligibility Review and Randomization

The Investigator or designee must document that the subjects meet each individual criterion (as outlined in Section 8.1 and Section 8.2) via a signed note or eligibility and clinical stability checklist during Screening. Signatures on these documents must be dated on or before the date of

Clinical Study Protocol Braeburn Pharmaceuticals HS-15-549 CONFIDENTIAL study start (Day 1). Prior to the first dose with CAM2038 q1w or CAM2038 q4w on Day 1, a recheck of the eligibility criteria will be performed.

Up to a total of 40 subjects will be randomized at a 3:2 ratio to Group 1 (CAM2038 q1w group with 24 subjects) Group 2 (128 mg CAM2038 q4w group with 16 subjects). Approximately 16 subjects will be enrolled into the additional Group 3 (24 mg SL BPN followed by 160 mg CAM2038 q4w).

Subjects randomized to Group 1 (CAM2038 q1w) will be randomized at a 1:1:1:1 ratio to 1 of the following 4 injection sequences: ABDC, BCAD, CDBA, and DACB, where A=buttock (reference), B=abdomen, C=thigh, and D=back of upper arm.

#### 10.3 Pharmacokinetic Assessments

#### **10.3.1 Drug concentration measurements**

### **10.3.1.1** Sample Collection, Preparation and Handling

PK samples for analysis will be collected at the time points specified in Table 1 (Group 1), Table 2 (Group 2), and Table 3 (Group 3).

The actual date and time of each PK sample collection will be recorded. The approximate total PK blood volume (6 mL per sample) to be taken per subject during the study is:

- Group 1 total PK blood volume = 342 mL
- Group 2 total PK blood volume = 204 mL
- Group 3 total PK blood volume = 276 mL

### **10.3.1.2** Determination of Drug Concentration

Plasma concentrations of BPN and norBPN will be determined using a validated LC-MS-MS method. The method is validated for a range of 0.0250 to 10.0 ng/mL for BPN and 0.0200 to 8.00 ng/mL for norBPN, based on the analysis of 0.500 mL of K2 EDTA plasma.

#### **10.3.2 Pharmacokinetic parameters**

Pharmacokinetic parameters of BPN and its active metabolite norBPN will be estimated using Phoenix® WinNonlin® (Certara, L.P., [name]), version 6.4 or higher. Standard non-compartmental methods and actual dates and times of dosing and blood sampling will be used in the calculations. The following PK parameters will be determined for BPN and norBPN (if applicable):

- Group 1:
  - $\circ$  AUCss (area under the plasma concentration-time curve during a 7-day dosing interval at steady state) for each injection site, i.e., buttock (reference), abdomen, thigh and back of upper arm.
  - $\circ$  Css,av for each injection site, i.e., buttock (reference), abdomen, thigh and back of upper arm.

- CONFIDENTIAL
   Css, max for each injection site, i.e., buttock (reference), abdomen, thigh and back of upper arm.
- $\circ$  tss,max for each injection site, i.e., buttock (reference), abdomen, thigh and back of upper arm.

 $\circ~$  norBPN/BPN ratios for AUCss and Css max for each injection site, i.e., buttock (reference), abdomen, thigh and back of upper arm.

• Group 2 and Group 3:

 $\circ$  AUCss (AUC during a 24-hour dosing interval at steady state for SL BPN [Group 3 only] and a 28-day dosing interval at steady state for CAM2038 q4w)

- o Css,av
- o Css,max
- o tss,max
- $\circ$  Css,28days (for CAM2038 q4w treatment) and Css,24h (for SL BPN treatment)
- $\circ \quad \text{norBPN/BPN ratios for AUC}_{\text{ss}} \text{ and } C_{\text{ss,max}}$

In Group 3, relative bioavailability of BPN will be assessed at steady state following repeated SC administration of 160 mg CAM2038 q4w as compared with repeated SL administration of 24 mg BPN.

Details of the PK evaluation will be presented in the statistical analysis plan (SAP). Values that are below the lower limit of quantification will be handled as described in the SAP.

### **10.4 Efficacy Assessments**

The following sections provide an overview of the exploratory efficacy assessments included in the study.

### **10.4.1 Urine Toxicology**

A 12-panel UDS will test for the following drugs of abuse: THC/marijuana, cocaine, phencyclidine (PCP), morphine and its related metabolites derived from opium (opiates), methamphetamines, methadone, amphetamines, barbiturates, benzodiazepines, methylenedioxymethamphetamine (MDMA), oxycodone and propoxyphene.

Urine drug screen samples will be collected at the time points specified in Table 1 (Group 1), Table 2 (Group 2), and Table 3 (Group 3) using a urine collection cup containing a temperature sensor. Specimen authenticity will be verified at the site using this sensor to measure the urine temperature immediately following collection. The temperature of a urine sample within 4 minutes of voiding should fall within the range of 32.2 to 37.7 degrees Celsius (90 to 100 degrees Fahrenheit). If test results are outside these ranges, the subject will be asked to immediately provide another urine sample. If this second sample is outside of the temperature range, the sample will be counted as 'missing', and should not be sent for analysis (any such samples must be documented in the subject's records). Direct observation approach to obtaining urine samples may be used if the Investigator deems necessary.

### 10.4.2 Numerical Rating Scale (NRS) for Pain

The NRS is an 11-point scale with anchors 0 (no pain) and 10 (worst pain imaginable). Subjects will record their Worst and Average Pain Score over the past 24 hours in an electronic diary on a daily basis. Study personnel and subjects will undergo training on how to complete the NRS assessment.

### **10.5** Safety Assessments

Safety monitoring will be performed throughout the study for all subjects. All AEs, regardless of causality or severity, will be recorded on the AE case report form (CRF). CAM2038 injections may be discontinued as clinically indicated.

### **10.5.1 Adverse Events and Serious Adverse Events**

#### **Adverse Event Reporting** 10.5.1.1

Throughout the study, AEs will be documented on the appropriate page of the CRF whether or not considered treatment-related. This includes any new signs, symptoms, injury or illness, including increased severity of previously existing signs, symptoms, injury, or illness. CAM2038 injections sites will be examined during each scheduled visits for any signs of adverse site reactions, including erythema, pruritus, edema, pain, etc. The new injection site will also be examined shortly minutes after each injection to determine if any site related AEs have occurred. Subjects will also be queried specifically about local tolerability AEs in connection to the examinations.

Conditions existing prior to dosing will be recorded as part of the subject's medical history. The Investigator is responsible for assessing the relationship of AEs to the study drug; relationship will be classified as not related, unlikely related, possibly related, or probably related (see Section 10.5.1.2 for definitions).

All AEs and SAEs will be collected by the Investigator from the time informed consent is signed until 7 days after the EOT visit. This includes any AEs that are ongoing at the completion/termination of the study, and any AEs that start after the last dose of study drug. SAEs and AEs that have been designated as possibly related to study drug will be followed until resolution or stabilization. Any SAEs considered related to study drug should be reported to the Sponsor without regards to these timelines.

Any SAE, including death resulting from any cause, which occurs to any subject participating in this study or within 14 days of the EOT visit or premature discontinuation from the study whether or not related to the study drug, must be reported via email, facsimile or telephone within 24 hours of first being advised of the SAE. Follow-up information collected for any initial report of an SAE must be reported to the Sponsor or designee within 24 hours of receipt by the Investigator. In the event discussion is necessary call the Medical Monitor.

The Sponsor or designee will determine whether the SAE must be reported within 7 or 15 days to the FDA. If so, the Sponsor (or the Sponsor's representative) will report the event to the FDA. The Investigator will transmit a written report of the circumstances and outcome to the Sponsor as soon Clinical Study Protocol Braeburn Pharmaceuticals HS-15-549 CONFIDENTIAL as he or she is made aware of the circumstances. The Investigator will report SAEs to the IRB per IRB policy.

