#### GROUP 3:

Each subject in Group 3 will participate in the study for up to 21 weeks, including up to approximately 3 weeks for screening, 17 weeks for treatment, and approximately 1 week for follow-up. Single daily doses of 24 mg SL BPN will be administered in the mornings on Day 1 through Day 7 for a total of 7 doses. This will be followed by SC injections of 160 mg CAM2038 q4w in the buttock, rotating between right and left buttock and injection site per Appendix 17.2, on Day 8, Day 36, Day 64 and Day 92, for a total of 4 doses. Following the first CAM2038 q4w administration, subjects will attend an interim visit on Day 9 to evaluate safety and tolerability of the transition from SL BPN to CAM2038 q4w.

Following administration of the first 3 doses of CAM2038 q4w, PK samples will be collected pre-dose and at scheduled times post-dose on an outpatient basis to determine achievement of steady state. To characterize steady state PK of BPN and norBPN and evaluate relative bioavailability CAM2038 q4w as compared with SL BPN, subjects will be confined to the CRU and serial PK samples will be collected for up to 24 hours following the seventh dose of SL BPN administered on Day 7, and following the fourth dose of CAM2038 q4w administered on Day 92. Subsequent PK samples will be collected up to 28 days post-dose on an outpatient basis.

At each study visit, safety and efficacy assessments will be conducted at pre-specified times. Subjects will also be required to record their worst daily pain and average daily pain using an 11-point NRS on an electronic device.

For all Groups, subjects will be transitioned to standard care as needed at the EOT or EOT-OLE visit, as applicable, and a follow-up call will be conducted approximately 7 days after the last study visit. Subjects who discontinue early will undergo EOT visit assessments, including PK sampling and urine toxicology.

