All efforts should be made by the Investigator to continue collection of concomitant medications, and AEs in subjects that discontinue study drugs, unless the subject withdraws his/her consent at the time of early discontinuation. Subjects discontinued due to clinically significant QTc interval prolongation should be monitored closely by undergoing daily ECGs, until ECG readings return to baseline, or QTc interval values are no longer judged to be clinically significant. The Investigator should also ask the subject to complete the Follow-up phone-call, provided that the subject has not withdrawn consent. If a subject refuses to complete EOT procedures and/or Follow-up, this information will be recorded.

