## 9.5 **Prior and Concomitant Therapy**

All non-study medications, including prescription, over-the-counter, or herbal therapies, used by the subject will be documented for the 30 days prior to Screening and throughout Version: 5.0, 05 OCT 2016 Page 35 of 87 Clinical Study Protocol Braeburn Pharmaceuticals HS-15-549 CONFIDENTIAL the study. The Investigator will determine if the prior/concomitant medication(s) affect the subject's eligibility to participate or continue to participate in the study. The following restrictions on concomitant medications will be in place during the study:

- Opioid receptors are likely to be occupied by BPN, which may reduce the analgesic effects of an opioid. The dissociation of BPN from the receptors may take several days following discontinuation of SL BPN treatment, or up to 2 weeks (Group 1) or up to a month (Group 2 [for subjects not entering the open-label extension] and Group 3) following the last CAM2038 injection. Therefore, subjects requiring analgesic emergency treatment or anesthesia for surgery should ideally be treated with a non-opioid analgesic. Opioids may be used with caution, but as higher doses may be required for analgesic effect, there may be a higher potential for toxicity with opioid administration. The clinical course should be carefully evaluated and fully documented for subjects who have a requirement for any opioid analgesic for >7 days continually or general anesthesia for surgery. Particular care should be taken in subjects with chronic respiratory disease, bowel disease and liver disease during anesthesia and the post-operative period.
- BPN is metabolized via CYP3A4. Because CYP3A4 inhibitors may increase plasma concentrations of BPN, if CYP3A4 inhibitors such as azole antifungals (e.g., ketoconazole), macrolide antibiotics (e.g., erythromycin), and HIV protease inhibitors (e.g., ritonavir, indinavir, and saquinavir) are required, the Medical Monitor must be consulted. Interactions with CYP3A4 inducers have not been investigated; therefore it is recommended that the use of agents such as phenobarbital, carbamazepine, phenytoin and rifampicin be avoided in subjects receiving study treatment. The Medical Monitor must be consulted prior to starting subjects on any of these agents.

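### AE collection ends 7 days after the EOT visit whatever the date of the last injection, so for an early q4w discontinuer it can end well inside the 28-day release period and the SAP's 30-day TEAE window

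*Protocol*

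**What the plan says.** Protocol 10.5.1.1 sets the end of collection: "All AEs and SAEs will be collected by the Investigator from the time informed consent is signed until 7 days after the EOT visit". Its next paragraph makes an SAE of any cause reportable if it occurs during the study or "within 14 days of the EOT visit or premature discontinuation from the study". Two sentences soften the cut-off: "SAEs and AEs that have been designated as possibly related to study drug will be followed until resolution or stabilization", and "Any SAEs considered related to study drug should be reported to the Sponsor without regards to these timelines".

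Section 7.1 says of early stoppers: "Subjects who discontinue early will undergo EOT visit assessments, including PK sampling and urine toxicology". For all groups, "a follow-up call will be conducted approximately 7 days after the last study visit". No section says how long after the last injection, or after the decision to stop, an early EOT visit takes place. Section 8.3 asks the investigator to make every effort to "continue collection of concomitant medications, and AEs in subjects that discontinue study drugs", unless consent is withdrawn. It gives no end date for this and names no contact for it beyond the follow-up call. Sections 8.3 and 10.5.5 require daily ECGs after a QTc discontinuation.

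On persistence, Section 5.1.2 describes q4w release over 4 weeks. Section 9.5 says dissociation of buprenorphine from its receptors may take "or up to a month (Group 2 [for subjects not entering the open-label extension] and Group 3) following the last CAM2038 injection".

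SAP 11.4 puts into the summary tables those TEAEs with onset before last dose + 30 days, as numbers and percentages of subjects.

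The Group 3 EOT visit is Day 120 in Table 3 (call on Day 127), but Day 127 in the protocol synopsis and in SAP 4.3.

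**The concern.** For completers, EOT falls one dosing interval after the last injection, so a rule tied to EOT works. For a subject who stops between injections, the EOT assessments come earlier in the interval and the same rule can close AE collection while the depot is still releasing drug.

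Safety and tolerability is a secondary objective, and each q4w group has about 16 subjects (Protocol 12.4), so one early stopper is 1/16, or about 6%, of a group. The SAP's percentages count a subject observed for 8 days after the last dose the same as one observed for 30. Days on which nobody was asked about AEs then count as days without events.

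The two SAE windows are a separate difficulty: a site cannot tell from the section whether an unrelated SAE 10 days after EOT is to be captured.

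**Working it through.** **Inputs.** Dosing, EOT and call days: Protocol Tables 1 to 3. Collection and SAE windows: 10.5.1.1. Release periods: 5.1.1 (q1w, 1 week) and 5.1.2 (q4w, 4 weeks = 28 days). TEAE tabulation window: SAP 11.4. Assumption: an early EOT visit takes place k days after the last injection, on the day of discontinuation; k is not in the documents, so a range is shown.

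**1. Reproduce the scheduled call (EOT + 7).** Group 1 extension 92 + 7 = 99; Group 2 extension 155 + 7 = 162; Group 3 120 + 7 = 127. All three match the tables.

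**2. Completers.** AE coverage after the last injection = EOT + 7 − last injection day. Any-cause SAE coverage is 7 days longer.

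| Subjects | AE coverage | SAE coverage |
|---|---|---|
| Group 1, no extension | 50 + 7 − 43 = 14 | 21 |
| Group 1, extension | 92 + 7 − 85 = 14 | 21 |
| Group 2, extension (last q1w Day 148) | 155 + 7 − 148 = 14 | 21 |
| Group 2, no extension | 113 + 7 − 85 = 35 | 42 |
| Group 3, EOT Day 120 | 120 + 7 − 92 = 35 | 42 |
| Group 3, EOT Day 127 | 127 + 7 − 92 = 42 | 49 |

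**3. Early q4w discontinuers.** AE coverage = k + 7; any-cause SAE coverage = k + 14. The AE shortfall is 21 − k days against 28, and 23 − k days against 30.

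| k | AE days | SAE days | AE short of 28 | AE short of 30 |
|---|---|---|---|---|
| 0 | 7 | 14 | 21 | 23 |
| 1 | 8 | 15 | 20 | 22 |
| 3 | 10 | 17 | 18 | 20 |
| 7 | 14 | 21 | 14 | 16 |
| 14 | 21 | 28 | 7 | 9 |
| 21 | 28 | 35 | 0 | 2 |
| 28 | 35 | 42 | 0 | 0 |

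Illustration with k = 1: a Group 3 subject injected on Day 8 has EOT assessments at the Day 9 visit. AE collection and the last scheduled contact end on Day 9 + 7 = Day 16. The any-cause SAE window ends on Day 9 + 14 = Day 23. The 28-day interval runs to Day 8 + 28 = Day 36.

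**4. q1w.** For any k, k + 7 is at least 7, so the window always covers the one-week release period. What remains is the SAP mismatch: 30 − 14 = 16 days after a final q1w injection. (The SAP says onset before day 30; read strictly, each shortfall against 30 is one day smaller.)

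**5. SAE windows.** 14 − 7 = 7 days: an unrelated SAE on days 8 to 14 after EOT is reportable under one paragraph, outside collection under the other, and later than the last planned contact.

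**The case against.** The best defence is that the protocol has other safeguards for these subjects. Section 8.3 asks for continued AE collection in exactly this group. Related SAEs have no time limit. Events already judged possibly related are followed to resolution or stabilization. QTc discontinuers have daily ECGs. All of this stands. It narrows the gap to new, non-ECG AEs and to SAEs judged unrelated. It does not close it: the request in 8.3 has no end date or planned contact and sits beside a fixed stop in 10.5.1.1, and a late event is reportable only if the site hears of it.

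A reader might infer more than the documents support:

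- That an early q4w stopper is followed for 8 days. That is the k = 1 case, close to the worst; no section times the early EOT visit.
- That subjects stopping for an AE or a QTc finding are observed least. The follow-to-resolution rule and the daily ECGs point the other way for those events.
- That Section 9.5 says the depot lasts up to a month. Its figure is for receptor dissociation; the release period is in 5.1.2.
- That the q4w safety profile will look better than it is. The documents give no expected number of early stops. The assessment schedules also mark a return to previous buprenorphine therapy at EOT, which would confound later opioid-type events.

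The 7- and 14-day sentences can be read as a collection window and a reporting window. That softens the conflict, but the 7-day sentence names SAEs, so the mismatch is real.

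**Conclusion.** The point holds in this form. The AE window follows the EOT visit rather than the last injection. For early q4w discontinuers it lasts k + 7 days: as little as 7 to 8, under 28 for every k below 21, and under the SAP's 30 for every k below 23. q4w completers are covered for 35 days (42 in Group 3 if EOT is Day 127) and are not affected. After a final q1w injection, collection runs 14 days against the SAP's 30. Section 10.5.1.1 gives two SAE windows 7 days apart, with no planned contact in the difference.

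This rests on EOT assessments being done at or near discontinuation, which the protocol implies but does not time. The direction of the risk is under-collection of late events; its size cannot be estimated from the documents. The sponsor should correct it because safety is a secondary objective, the groups are small and the repair is cheap.

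**What to change.** 1. In Protocol 10.5.1.1, 7.1 and 8.3, end AE collection at the later of EOT + 7 days and a stated interval after the last injection. For q4w this should cover the release period and match the SAP: for example 30 days, or the 35 days completers already receive. Give 8.3 the same end date, and say when the early EOT visit takes place.
2. Keep the 7-day call and add one call at the end of the window for early discontinuers. Moving the existing call instead would remove early contact: in the Day 8/Day 9 example with 35 days, from Day 16 to Day 8 + 35 = Day 43.
3. State one SAE window, never shorter than the present 14 days after EOT or discontinuation. Using the completers' AE interval for SAEs would cut any-cause reporting from 42 to 35 days after the last q4w injection and from 21 to 14 after the last q1w injection.
4. In SAP 11.4, reconcile the 30-day tabulation window with collection for q1w, and with q4w if 35 days is chosen.
5. Reconcile the Group 3 EOT day (120 or 127), since the windows are counted from it.

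Cost: wording changes, one extra phone call per early discontinuer, and follow-up longer by at most 35 − 7 = 28 days (30 − 7 = 23 with the 30-day option) for early q4w discontinuers. If q1w collection is lengthened rather than the SAP window shortened, q1w subjects also stay longer.
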